9.4.2 Hypoglycemia

Hypoglycemic events will be appropriately recorded in the CRF. In the case of a hypoglycemic event, the actual blood glucose value, if measured, will be recorded in the CRF, together with any treatments administered. Each category of hypoglycemic events (defined below) will be listed and summarized by treatment. Hypoglycemia is defined as follows:

- **Documented Glucose Alert Level (Level 1), Plasma Glucose (PG) ≤ 70 mg/dL (3.9 mmol/L):**
 - **Symptomatic hypoglycemia:** an event during which typical symptoms of hypoglycemia are accompanied by PG ≤ 70 mg/dL (3.9 mmol/L)
 - **Asymptomatic hypoglycemia:** an event not accompanied by typical symptoms of hypoglycemia but with PG ≤ 70 mg/dL (3.9 mmol/L)
 - **Unspecified hypoglycemia:** an event during which PG ≤ 70 mg/dL (3.9 mmol/L) but no information relative to symptoms of hypoglycaemia was recorded
- **Documented Clinically Significant Hypoglycemia (Level 2) PG ≤ 54 mg/dL (3.0 mmol/L):**
 - **Symptomatic hypoglycemia:** an event during which typical symptoms of hypoglycemia are accompanied by PG ≤ 54 mg/dL (3.0 mmol/L)
 - **Asymptomatic hypoglycemia:** an event not accompanied by typical symptoms of hypoglycemia but with PG ≤ 54 mg/dL (3.0 mmol/L)
 - **Unspecified hypoglycemia:** an event during which PG ≤ 54 mg/dL (3.0 mmol/L) but no information relative to symptoms of hypoglycemia was recorded.
- **Severe hypoglycemia (Level 3):** an event requiring the assistance of another person to actively administer carbohydrate, glucagon, or other resuscitative actions. During these episodes, the subject has an altered mental status and cannot assist in their care, is semiconscious or unconscious, or experienced coma with or without seizures and may require parenteral therapy. Plasma glucose measurements may not be available during such an event, but neurological recovery attributable to the restoration of blood glucose concentration to normal is considered sufficient evidence that the event was induced by a low PG concentration (≤ 70 mg/dL [3.9 mmol/L]).
 - **Severe hypoglycemia requiring medical attention:** a severe hypoglycemic event when subjects require therapy by health care providers (emergency medical technicians, emergency room personnel, etc.).

Other Hypoglycemia:

- **Nocturnal hypoglycemia:** any hypoglycemic event (documented symptomatic, asymptomatic, probable symptomatic, or severe hypoglycemia) that occurs between bedtime and waking
- **Relative hypoglycemia:** an event during which typical symptoms of hypoglycemia, which do not require the assistance of another person, are accompanied by PG

>70 mg/dL (3.9 mmol/L), but these levels may be quickly approaching the 70 mg/dL (3.9 mmol/L) threshold

- **Overall (or total) hypoglycemia:** this optional category combines all cases of hypoglycemia. If an event of hypoglycemia falls into multiple subcategories, the event is counted only once in this category
- **Probable symptomatic hypoglycemia:** an event during which symptoms of hypoglycemia are not accompanied by a PG measurement but that was presumably caused by PG ≤ 70 mg/dL (3.9 mmol/L).

Investigator review of glucose results clinically indicative of hypoglycemia will be required.

9.4.3 Concomitant Medication

Concomitant medication will be coded using the WHO drug dictionary (Version September 2019). Concomitant medication will be listed.

9.4.4 Clinical Laboratory Parameters

All clinical chemistry and hematology data will be summarized by parameter and treatment, and listed. Urinalysis data will be listed. Changes from baseline (Day -1 in the lead-in phase) will also be presented. Additionally, clinical chemistry, hematology and urinalysis data outside the reference ranges will be listed and flagged on individual subject data listings.

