5. STUDY DESIGN

This is a single-center, open-label, 2-period, fixed sequence study with a lead-in period, in healthy female subjects. Subjects may already have been on OC medication prior to screening or be OC naïve. Potential subjects will be screened to assess their eligibility to enter the study within 28 days prior to Day 1 of the lead-in period. A final follow-up visit will occur on Day 49 ± 1 day (i.e. 28 days ± 1 day after tirzepatide dosing). During each treatment period, the PK of individual components of the OC combination will be assessed on Day 21 to enable evaluation

of OC PK alone. During period 2, tirzepatide will be administered on Day 20 such that peak exposure by Day 21 (tirzepatide time of maximum observed drug concentration [t_{max}] ~ 24 hours postdose) can be attained when OC PK is evaluated on Day 21 (norgestimate [NGM] and ethinyl estradiol [EE] are rapidly absorbed after oral administration). This will permit studying the influence of tirzepatide on OC PK, in the presence of maximum exposure; i.e. with greatest impact on gastric emptying (GE).

Figure GPGR.1 illustrates the study design.

Abbreviations: Adm = admission to the clinical research unit; CRU = clinical research unit; Dis = discharge from the clinical research unit; OC = oral contraceptive; PK = pharmacokinetic

Figure GPGR.1. Illustration of study design

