7. SAMPLE SIZE JUSTIFICATION

Approximately 42 subjects will be enrolled so that a minimum of 28 subjects complete the study.

For EE area under the concentration versus time curve (AUC) and maximum observed drug concentration (C_{max}), the intra-subject variability (coefficient of variation [CV]) was estimated to be 18.2% and 14.2%, respectively (derived from study H9X-MC-GBCQ). Based on this assumption, 28 subjects will provide a precision of 0.10 and 0.08 on a log-scale for AUC and C_{max} , respectively. This would result in a 90% probability that the half-width of the 90% confidence interval (CI) of the ratio of geometric least square means for AUC and C_{max} is no larger than 9.3% and 7.3%, respectively.

For norelgestromin (NGMN) AUC and C_{max} , the intra-subject variability (CV) was estimated to be 16.3% and 20.0% respectively (derived from study H9X-MC-GBCQ). Based on this assumption, 28 subjects will provide a precision of 0.09 and 0.11 on a log-scale for AUC and C_{max} , respectively. This would result in a 90% probability that the half-width of the 90% CI of the ratio of the geometric least square means for AUC and C_{max} is no larger than 8.3% and 10.2%, respectively.

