9.4 Safety and Tolerability Assessments

9.4.1 Adverse Events

A pre-existing condition is defined as an adverse event (AE) that starts before the subject has provided written informed consent and is ongoing at consent. A non-treatment emergent AE is defined as an AE which starts after informed consent but prior to OC dosing in the lead-in phase. A treatment-emergent AE is defined as an AE which occurs postdose or which is present prior to dosing and becomes more severe postdose.

The assignment of TEAEs to treatments will be as follows:

- A TEAE occurring during or after Day 1 dosing in the lead-in phase and prior to tirzepatide dosing on Day 20 in Period 2 will be assigned to OC.
- A TEAE occurring during or after tirzepatide dosing on Day 20 in Period 2 will be assigned to OC + 5 mg tirzepatide SC.

Where changes in severity are recorded in the Case Report Form (CRF), each separate severity of the AE will be reported in the listings. The following rules will be applied in summary tables:

- If an AE increases in severity, the AE will only be counted once at the maximum severity with the exception of the following:
 - If an AE occurs during or after Day 1 dosing in the lead-in phase and increases in severity during or after tirzepatide dosing on Day 20 in Period 2; the AE will be counted twice (at the maximum severity for each treatment).
- If an AE decreases in severity at any time, the AE will be counted once at the maximum severity.

All AEs will be listed. Treatment-emergent AEs will be summarized by treatment (including overall), severity and relationship to the study drug. The frequency (the number of AEs, the number of subjects experiencing an AE and the percentage of subjects experiencing an AE) of treatment-emergent AEs will be summarized by treatment, Medical Dictionary for Regulatory Activities (MedDRA) version 22.1 system organ class and preferred term. The summary and frequency AE tables will be presented for all causalities and those considered related to the study drug by the investigator. Any serious AEs will be listed. AEs by day of onset will be presented.

Discontinuations due to AEs will be listed.

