9.4.5 Serum Progesterone

Compliance with the OC during the lead-in period will be assessed by serum progesterone testing on Day 21 of the lead-in period. These data will be listed.

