9.4.14 Safety and Tolerability Statistical Methodology

No inferential statistical analyses are planned.

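### Does taking laboratory change only from lead-in Day -1 leave the tirzepatide step hidden in the safety tables?

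*SAP*

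**What the plan says.** Section 9.4.4 of the SAP plans the laboratory summaries in two parts. The first is "All clinical chemistry and hematology data will be summarized by parameter and treatment, and listed". The second is "Changes from baseline (Day -1 in the lead-in phase) will also be presented". Section 9.1 defines each change as the value at a timepoint minus that subject's baseline value. Values outside the reference range are also listed and flagged.

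Section 5 describes a fixed-sequence design with an OC lead-in and two periods, with tirzepatide given once, on Day 20 of Period 2. On entry status it says "Subjects may already have been on OC medication prior to screening"; OC-naive subjects are also eligible.

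Two other sections use the tirzepatide dose as a dividing point. Section 9.4.1 assigns adverse events to OC before that dose and to OC plus tirzepatide from it onward. Section 9.4.9 takes the predose sample on that day as baseline for anti-drug antibodies.

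Section 9.4.14 says of safety and tolerability: "No inferential statistical analyses are planned". Section 3 leaves the detailed description of the tables to a separate shell document.

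**The concern.** The secondary objective concerns the safety of one tirzepatide dose given with an OC, so a reader naturally wants the laboratory change from just before that dose to after it. With Day -1 as the only baseline, the change under OC plus tirzepatide spans the whole OC exposure as well. The baseline also mixes women already taking an OC with women who were not. A shift caused by starting the OC could be mistaken for a tirzepatide effect, or could mask one.

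Subtracting the OC mean change from the OC plus tirzepatide mean change looks like an easy repair. It may mislead if different subjects contribute to the two means, and section 7 allows for sizeable loss: "Approximately 42 subjects will be enrolled so that a minimum of 28 subjects complete the study". The spread of the within-subject step cannot be recovered from the two standard deviations at all.

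The adverse event rules seem to point the same way. An event that starts on OC and "increases in severity during or after tirzepatide dosing on Day 20 in Period 2; the AE will be counted twice", once per treatment, which suggests that the SAP treats the tirzepatide dose as a second starting point there but not for laboratory data.

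**Working it through.** The SAP gives no figure for this point, so there is none to reproduce. The check asks what the reported change contains, how far a reader could be misled, and whether any conclusion depends on it.

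**Time between baseline and tirzepatide.** The lead-in lasts at least 21 days, because section 9.4.5 has "serum progesterone testing on Day 21 of the lead-in period". Period 1 lasts at least 21 days, because section 5 says "During each treatment period, the PK of individual components of the OC combination will be assessed on Day 21". Day 20 of Period 2 is 19 days after its Day 1. From the first study OC dose to tirzepatide is therefore at least 21 + 21 + 19 = 61 days. If the cycles are 28 days (an assumption), it is 28 + 28 + 19 = 75 days.

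**What the reported change contains.** Let B be the Day -1 value, O the last value on OC before tirzepatide, and T the value after tirzepatide. Put a = O - B and d = T - O. The change under OC plus tirzepatide is T - B = a + d, which equals d only if a = 0. With assumed shifts in arbitrary units:

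| a | d | Change from Day -1 | Change from pre-tirzepatide value |
|---|---|---|---|
| +5 | 0 | 5 | 0 |
| -5 | +5 | 0 | 5 |
| 0 | +5 | 5 | 5 |

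The decomposition is correct. It shows that T - B and T - O answer different questions. It does not show that T - B is wrong.

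**Error from subtracting mean changes.** Suppose 42 subjects have an O value and only the 28 completers have a T value. Then

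mean28(T - B) - mean42(O - B) = mean28(T - O) + [mean28(O - B) - mean42(O - B)].

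Let g be the mean OC change in completers minus that in non-completers. Since mean42 weights the groups 28/42 and 14/42, the bracket equals (14/42) × g = 0.33g. If only 7 non-completers have an O value, it is (7/35) × g = 0.20g. If none has, it is 0. The SAP gives no g, and nothing in it suggests that laboratory change on OC differs by completion status.

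**Spread of the step.** If O - B and T - B both have standard deviation s and correlation r, then SD(d) = s × √(2(1 - r)):

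- r = 0.2: s × √1.6 = 1.26s
- r = 0.5: s × √1.0 = 1.00s
- r = 0.8: s × √0.4 = 0.63s

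The planned summaries do not report r, so this spread cannot be read from them. The r values are assumed.

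**What depends on d.** No test, interval, margin or decision rule in the SAP uses the mean or SD of a laboratory step. Raw values are summarized separately for OC and for OC plus tirzepatide, so a shift between treatments is visible without any baseline. Each subject's values are listed, so the step can be worked out wherever both samples exist. Section 9.4.10 adds separate confirmation and listings for raised liver tests.

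**Comparison with the other sections.** The adverse event rule in section 9.4.1 assigns events to treatments so that each treatment's count is complete; it does not define a baseline. Its laboratory counterpart is the summary by treatment, which section 9.4.4 already has. The antibody baseline differs for a plain reason: antibodies to tirzepatide are judged against the state before tirzepatide, whereas laboratory values may respond to the OC too. A pre-OC baseline suits the second case and a pre-tirzepatide baseline the first. Section 9.4.6 plans no change from baseline for vital signs at all, which fits deliberately light descriptive safety reporting.

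**The case for a change.** The best argument for the concern is that the step after tirzepatide is the quantity closest to the secondary objective, that section 9.4.4 names no summary of it, and that one sentence and one table would supply it. The algebra behind this stands. So does the point that the two mean changes cannot give the SD, median or range of the step, even when the same subjects contribute to both.

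The step from there to a defect does not stand. The argument accepts Day -1 as a legitimate baseline and would keep it, so nothing in the plan would be corrected. The 0.33g figure is an extreme: it needs all 14 possible non-completers to have a laboratory value on OC, none to have one after tirzepatide, and their OC changes to differ from those of completers. The 42 and 28 in section 7 are an enrolment target and a floor for completers, not a forecast of missing laboratory data.

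The proposed table also rests on things the SAP does not show. The laboratory schedule belongs to the protocol, and the summary by treatment suggests on-OC samples before tirzepatide without establishing them. The table shells could already contain such a column. Finally, with every subject receiving tirzepatide last and no concurrent control, change from the later reference would still mix tirzepatide with time, only over a shorter interval.

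**Conclusion.** The concern does not hold. Section 9.4.4 fixes a single, clearly stated laboratory baseline that precedes all study treatment and serves both treatments alike. Followed exactly, it gives a sound descriptive account of laboratory values on OC and on OC plus tirzepatide. The reported change under OC plus tirzepatide should be read as the change over the whole regimen, including at least 61 days from the first OC dose to tirzepatide, and not as a tirzepatide effect.

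The largest distortion identified is 0.33g in an informal subtraction that the SAP does not plan, with a range that reaches 0. Both g and r are assumptions. The primary pharmacokinetic analysis, the sample size and every planned inference are unaffected. A supplementary change from the last pre-tirzepatide value would be a reasonable preference where the schedule allows it, but its absence is no error. This conclusion rests on the SAP alone, without the protocol's laboratory schedule or the table shells; neither could turn the stated baseline into an error.

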9.4.5 Serum Progesterone

Compliance with the OC during the lead-in period will be assessed by serum progesterone testing on Day 21 of the lead-in period. These data will be listed.

9.4.6 Vital Signs

Vital signs data will be summarized by treatment and timepoint. Values for individual subjects will be listed.

Temperature will be listed only.

9.4.7 Body Weight and Height

Body weight and height will be listed.

9.4.8 Electrocardiogram (ECG)

ECGs will be performed for safety monitoring purposes only and will not be presented. Any clinically significant findings from ECGs will be reported as an AE.

9.4.9 Immunogenicity Assessments

Immunogenicity data will be listed and frequency tables will be presented. The frequency and percentage of subjects with pre-existing anti-drug antibody (ADA) and with treatment-emergent

ADAs (TE ADAs) will be presented. TE ADAs are those that are boosted or induced by exposure to study drug, with a 4-fold increase in titer compared to baseline if ADAs were detected at baseline or a titer 2-fold greater than the minimum required dilution (1:10) if no ADAs were detected at baseline, where baseline is defined as Day 20 predose in Period 2.

If cross-reactivity with native GLP-1 and GIP or a neutralization assay is performed, the frequency of each will be determined.

The relationship between the presence of antibodies and PK parameters of tirzepatide may be assessed if deemed appropriate.

9.4.10 Hepatic Monitoring

If a subject experiences elevated alanine aminotransferase (ALT) $\geq 3 \times$ upper limit of normal (ULN), alkaline phosphatase (ALP) $\geq 2 \times$ ULN, or elevated total bilirubin (TBL) $\geq 2 \times$ ULN, liver tests will be performed to confirm the abnormality. Additional safety data may be collected if required, as defined in the protocol. Where applicable, the following will be presented.

The subjects' liver disease history and associated person liver disease history data will be listed. Any concomitant that have potential for hepatotoxicity, including acetaminophen will be listed. Results from any hepatic monitoring procedures, such as a magnetic resonance elastography (MRE) scan, and biopsy assessments will be listed, if performed.

Hepatic risk factor assessment data will be listed. Liver related signs and symptoms data will be summarized by treatment and listed. Alcohol and recreational drug use data will also be listed.

All hepatic chemistry, hematology, coagulation, and serology data will be listed. Values outside the reference ranges will be flagged on the individual subject data listings.

9.4.11 Hypersensitivity Reactions

For all drug hypersensitivity reactions that occur, additional follow-up data will be collected to assess the subject's medical history, alternative causes, and symptoms.

These data will be listed.

9.4.12 Injection-Site Reactions

Injection-site assessments for local tolerability will be conducted, when reported as:

- an AE from a subject, or
- a clinical observation from an investigator.

Injection site assessment data (erythema, induration, categorical pain, pruritus, and edema) will be listed.

9.4.13 Other Assessments

All other safety assessments not detailed in this section will be listed but not summarized or statistically analyzed.

9.4.14 Safety and Tolerability Statistical Methodology

No inferential statistical analyses are planned.

10. INTERIM ANALYSES

No interim analyses are planned for this study.

11. CHANGES FROM THE PROTOCOL SPECIFIED STATISTICAL ANALYSES

There were no changes from the protocol specified statistical analyses.

13. DATA PRESENTATION

13.1 Derived Parameters

Individual derived parameters (e.g. PK parameters) and appropriate summary statistics will be reported to three significant figures. Observed concentration data, e.g. C_{max} , should be reported as received. Observed time data, e.g. t_{max} , should be reported as received. N and percentage values should be reported as whole numbers. Median values should be treated as an observed parameter and reported to the same number of decimal places as minimum and maximum values.

13.2 Missing Data

Missing data will not be displayed in listings.

